Three count numbers are used by the decision rule and are defined as follows.

- Titration-Dose Evaluable Subjects (nH): the number of subjects who are titrated and complete the evaluation period (2 weeks) starting from the first titration dose (on day 43).
- Start-Dose Evaluable Subjects (nL): the number of subjects who develop drug related SAE at grade 3 or higher or complete the evaluation period (2 weeks) from the first dose (on day 1) but haven't completed the 2 weeks evaluation period following the first titration dose (on day 43) if being titrated to a higher dose.

- Subjects with AE of Interest (k): the largest number of subjects who developed drug related SAE within the same organ system at grade 3 or higher, which could happen any time after the first dose of BMS-986004 till the decision making day. The value of k is allowed to be either 0 or 1. Note that it doesn't distinguish at which stage of treatment, prior to or post titration, that such AE happened.

Minimum Requirement for Cohort Escalation

A set of minimum safety requirement, as listed below, must be met in order to make an early decision.

- There must be at least 5 (nL+nH>=5) safety evaluable subjects (with safety data through study Day 15)
- A higher dose than the new cohort's start dose must be shown tolerated in the IM140-002 study.

Early Decision Rule:

If there is not AE of interest observed, the early decision rule is the same as the minimum requirements.

If there is one AE of interest observed, the early decision rule is shown in [Table 3.1.4-1](#), where W represent wait, i.e., not enough evidence to enable dose panel escalation, and E represents escalate.

If there are least two subjects with AE of interest, stopping rule is triggered, and subject cannot be treated at the next higher cohort.

Study Population:

Male and Female subjects ≥ 18 years old with persistent or chronic ITP according to American Society of Hematology (ASH), with or without prior splenectomy guidelines will be eligible to participate in the study.

Women of childbearing potential (WOCBP) must not be nursing or pregnant and must be using an acceptable method of contraception for at least 4 weeks before dosing. WOCBP must have a negative pregnancy test within 24 hours prior to dosing with study medication

Study Drug includes both Investigational [Medicinal] Products (IP/IMP) and Non-investigational [Medicinal] Products (Non-IP/Non-IMP) as listed:

Study Drug for BMS-986004

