3.1.1 Intra-subject dose escalation

Intra-subject dose escalation could occur after the subject has completed the Response Phase of the study. The intra-subject dose escalation decision will be based on review of the safety information and platelet count after 4 weeks of treatment. The decision to escalate dose for the subject will be made after evaluating platelet count at Day 50, 7 days after the 4th dose of BMS-986004 has been administered. Subject will receive the next higher dose of BMS-986004 if clinically significant response has not been achieved based on measurement of platelet count on

the last two consecutive counts performed at Day 43 and Day 50, and a favorable safety profile is observed (see Table 3.1.1-1). Clinically significant response is defined as achieving platelet count $\geq 50,000/\text{mm}^3$ with an increase of at least $20,000/\text{mm}^3$ from baseline and absence of bleeding. Subject will then be dosed at the higher dose level for the remainder of the study (Remission Phase), receiving investigational product at that dose on Week 8, Week 10 and Week 12. Active treatment period with BMS-986004, regardless of the dose, may not exceed 12 weeks for any individual subject.

Table 3.1.1-1: Dose Adjustment after Response Phase

Platelet Count at Day 43 and Day 50 (7 days after the 4th dose) (X /mm³)	Action
< 50,000	Dose increase, as indicated by the next dose panel
$\geq 50,000$ with an increase of at least 20,000 from baseline	Dose remains constant on bi-weekly schedule

3.1.2 Dose frequency adjustment for responders exceeding 450,000/mm³ (for non-splenectomized subjects) and 600,000/mm³ (for splenectomized subjects) platelet count

For both the Short Term Study and the Long Term Extension plan, in the event that platelet count exceeds $450,000/\text{mm}^3$ for non-splenectomized subjects and $600,000/\text{mm}^3$ for subjects who underwent splenectomy, in the absence of recent (administered within two weeks) rescue medication, as indicated by the two consecutive platelet count measurements, dosing of the BMS-986004 should be stopped. Subject will remain in the study and platelet counts will be then assessed based on the normal study visit schedule. Dosing of BMS-986004 could be reinitiated only after discussion between Study Director and Investigator if clinically appropriate and dictated by the medical judgment and subject’s safety.

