3.1.4 Early decision of dose escalation for dose panel

When a cohort is filled and a new subject is available to be treated, an early decision can be made on whether to open the next higher cohort if not all the subjects have completed the evaluation period. The early decision rule is based on controlling the probability of making a wrong early decision, called decision risk, to be at most 15%. Detailed information on deriving the decision risk is included in [Appendix 1](#).

The early decision rule is based on the largest number of subjects who developed AE of interest which is drug-related SAE within the same organ system at grade 3 or higher. The early decision does not directly take into consideration other criteria as covered by the stopping rule. As such, its decision can be modified upon agreement from both investigators and sponsor. In case subjects are allocated to the higher cohort and at least one stopping rule as stated above is triggered toward the lower dose cohort when more events are observed at the lower cohort, decision will be made upon agreement from both investigators and sponsor after considering all safety data.

Three count numbers are used by the decision rule and are defined as follows.

- Titration-Dose Evaluable Subjects (nH): the number of subjects who are titrated and complete the evaluation period (2 weeks) starting from the first titration dose (on day 43).
- Start-Dose Evaluable Subjects (nL): the number of subjects who develop drug related SAE at grade 3 or higher or complete the evaluation period (2 weeks) from the first dose (on day 1) but haven't completed the 2 weeks evaluation period following the first titration dose (on day 43) if being titrated to a higher dose.
- Subjects with AE of Interest (k): the largest number of subjects who developed drug-related SAE within the same organ system at grade 3 or higher, which could happen any time after the first dose of BMS-986004 till the decision making day. The value of k is allowed to be either 0 or 1. Note that it doesn't distinguish at which stage of treatment, prior to or post titration, that such AE happened.

Minimum Requirement for Cohort Escalation

A set of minimum safety requirement, as listed below, must be met in order to make an early decision.

- There must be at least 5 (nL+nH>=5) safety evaluable subjects (with safety data through study Day 15)
- A higher dose than the new cohort’s start dose must be shown tolerated in the IM140-002 study.

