APPENDIX 1 ADAPTIVE EARLY DECISION FOR DOSE PANEL ESCALATION

Introduction

A model-based cohort escalation rule is established to help decide on opening the next cohort for newly enrolled subjects when current cohort is filled but not all of its subjects are monitored for 2 whole weeks regarding drug toxicity and tolerability. The decision rule would allow treating subject, once available, at the next cohort without waiting for the completion of every subject's AE evaluation period at the current cohort and at the same time keeping decision risk acceptably low.

Please note that AE would be closely monitored throughout the trial for each subject, and the 2 weeks' AE evaluation period mentioned here is for the purpose of cohort escalation only. During the evaluation period, the numbers of subjects who developed drug-related SAE within the same organ system at grade 3 or higher, called AE of interest are counted and the largest number will be used.

Decision Risk

The decision risk is mathematically defined as the probability of observing enough number of event(s) in the still non-evaluable subjects given data collected from evaluable subjects such that cohort escalation is not allowed. Evaluable subjects are those who are observed an AE of interest or complete the AE evaluation period. To enroll subject into the next cohort, the non-adaptive cohort escalation rule requires, among others, no more than one subject being reported drug-related serious adverse event or serious infection and infestation within the evaluation period. Therefore, if one subject is observed with an AE of interest, the decision risk would be the probability of observing at least one more AE of interest in the non-evaluable subjects; if no AE of interest is reported, the decision risk is thus the probability of observing at least two AEs of interest from the non-evaluable subjects.

Decision Data

To take advantage of the titration design, in which subjects could possibly take a higher dose that is to be used initially in the next cohort, the adaptive decision rule makes use of the following three statistics:

- Titration-Dose Evaluable Subjects (nH): the number of subjects who are titrated and complete the evaluation period (2 weeks) starting from the titration's first dose (on day 43).

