- Start-Dose Evaluable Subjects (nL): the number of subjects who develop drug related SAE at grade 3 or higher or complete the evaluation period (2 weeks) from the first dose (on day 1) but haven't completed the 2 weeks evaluation period following the first titration dose (on day 43) if being titrated to a higher dose.
- Count of AE of Interest (k): number of subjects with AE of interests, which could happen any time after the first dose of BMS-986004 till the decision making day. Apparently, $k=0$ or 1. Please note that it doesn't distinguish at which stage, prior to or post titration, that such AE happened.

With sample size of 10 for each cohort, the number of non-evaluable subjects is $10-nH-nL$.

Decision Risk Estimation

Calculation of decision risk is based on the method of Bayesian constrained rate estimate with ascending beta prior. It assumes that the rate of AE of interest increases with doses, however, no specific mathematical form is given governing the relationship between dose and rate. In this way, robustness is achieved by avoiding possible model misspecification. It also assumes that rate depends on the maximum dose subject takes, i.e., titrated subjects are equally likely in developing AE of interest as subjects who take the titrated dose right in the beginning. The prior information is solicited from a phase III study of Abatacept IM101174, in which 12 out of 721 subjects (1.7%) were reported to experience drug related SAEs within short term period (half year treatment). The prior used is Beta(0.01, 0.49), which indicates 2% rate and is equivalent of contributing 0.5 subject at each dose.

Decision risk for $k=1$ is listed below (values are provided only for when the number evaluable subjects, $nH+nL$, is at least 5, and at most 9). Bayesian MCMC simulation is performed to compute the posterior predictive probability under R version 3.1.0 with a random seed of 20140625.

Titration-Dose Evaluable Subjects (nH)	Start-Dose Evaluable Subjects (nL)								
	1	2	3	4	5	6	7	8	9
0					43.2	34.1	25.4	16.6	8.3
1				38.6	30.0	22.7	14.6	7.2	
2			36.0	29.1	21.1	13.9	6.8		
3		34.9	27.4	20.0	13.1	6.5			
4	33.9	25.9	19.3	12.9	6.2				
5	25.7	19.3	12.5	6.0					
6	18.4	11.9	5.9						
7	11.8	5.7							
8	5.7								

When $k=0$, decision risk is close to zero, therefore not provided.

Minimum safety requirement:

Other conditions, as listed below, have to meet to open a new cohort

There must be at least 5 evaluable subjects

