2 STUDY DESCRIPTION

2.1 Study Design

This is a Phase 1b/2, multicenter, open-label, MAD study to evaluate the safety, efficacy, dose response, and pharmacology (PK, target engagement and PD) of BMS-986004 administered every 2 weeks in subjects with ITP.

Figure 2.1-1: Study Design Schematic

[figure not shown]
The study is divided into screening (3 weeks), response phase (6 weeks), remission phase (6 weeks) and follow up period (4 weeks). Forty subjects are treated in 4 dose panels, 75mg, 225mg, 675mg, and 1500mg, of 10 subjects each. BMS-986004 will be administered on day 1, 15, 29, 43, 57, 71, 85, a total of 7 doses as IV infusion. Four (4) doses will be administered during the Response Phase over a 6 week treatment period. The remaining 3 doses will be administered during the Remission Phase of the study over a 6 week treatment period. The study design schematic is presented in Figure 2.1-1.

Cohort of lower than 75mg or intermittent dose may be opened.

Intra-subject dose escalation

Subject may be dosed at a higher dose beginning from day 57 for the remainder of the study if clinically significant response has not been achieved at Day 43 and Day 50, and a favorable safety profile is observed.

Figure 2.1-2: Decision Rule on Intra-Subject Dose Escalation

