7.7 Pharmacokinetics

PK sampling date and time are shown below in [Table 7.7-1](#) for convenience. On day 57, non-responders in each treatment group other than the 1500mg group will be dose-escalated to the starting dose of the next higher treatment group.

The Pharmacokinetic (PK) population will be used for all listings. Evaluable PK population will be used for summaries. PK parameters and C_{trough} will be summarized for each group decided by current dose, and dose proportionality analysis will be provided by excluding subjects who have dose escalation on day 57.

Table 7.7-1: PK Sample Study Day and Time

study day	dosing	PK Sampling
1	#1, at starting dose	0h, 2h, 24h, 72h, 168h
15	#2, at starting dose	0h
29	#3, at starting dose	0h
43	#4, at starting dose	0h, 168h
57	#5, Responder: at starting dose Non-Responder: at titration dose	0h, 2h
71	#6, at the same dose as Day 57	0h, 2h, 24h, 96h, 168h
85	#7, at the same dose as Day 57	0h, 336h, 672h

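### The early cohort-escalation rule dates the first higher dose to Day 43 when it is given on Day 57, and applying the printed day can turn Wait into Escalate above the 15% risk cap

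*Protocol*

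**What the plan says.** Protocol 3.1.4 lets the next panel open before all 10 subjects in the current one have been observed for two weeks, provided the decision risk is at most 15%. With one subject having an AE of interest (k=1), the decision is read from Table 3.1.4-1 using two counts:

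- nH, the titration-dose evaluable subjects: "the number of subjects who are titrated and complete the evaluation period (2 weeks) starting from the first titration dose (on day 43").
- nL, the start-dose evaluable subjects. These include titrated subjects who have not yet completed the "evaluation period following the first titration dose (on day 43) if being titrated to a higher dose".

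The same day appears in both definitions in the synopsis, 3.1.4 and Appendix 1. The footnotes to Table 3.1.4-1 name no day.

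The dosing sections give a different date. Protocol 3.1.1: "The decision to escalate dose for the subject will be made after evaluating platelet count at Day 50, 7 days after the 4th dose"; the subject then continues "receiving investigational product at that dose on Week 8, Week 10 and Week 12". SAP 2.1: "Subject may be dosed at a higher dose beginning from day 57 for the remainder of the study". SAP 7.7: "On day 57, non-responders in each treatment group other than the 1500mg group will be dose-escalated". SAP Table 7.7-1 lists Day 43 as the fourth dose, at the starting level, and Day 57 as the first dose at the titrated level.

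**The concern.** A subject cannot receive a higher dose on Day 43 when the decision to give it waits for the Day 50 count. The printed day is therefore wrong, and it moves subjects from nL to nH two weeks too soon.

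This matters because nH lowers the computed risk. Appendix 1 assumes that the event rate rises with dose and depends on the highest dose a subject has taken. An event-free subject in nH is therefore treated as evidence that the higher dose, and so the lower one too, is tolerated. A subject on Day 57 has only just received the first higher-dose infusion and supplies no such evidence.

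The k=1 table is used after a drug-related SAE of grade 3 or higher, to decide whether new subjects start at a higher dose before the current panel is fully observed. If the wrong count is fed in, the rule can permit escalation at a risk that its own table puts above its stated cap.

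**Working it through.** **Dates.** Weeks 8, 10 and 12 are Days 57, 71 and 85.

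- Printed rule: 43 + 14 = Day 57, so the subject enters nH on Day 57.
- Actual dosing: 57 + 14 = Day 71, so the subject should enter nH on Day 71.
- On Days 57 to 70 the subject is misclassified, with 57 − 57 = 0 to 70 − 57 = 13 days since the first higher dose.

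**Reproducing the risk table.** Inputs from Appendix 1: cohort of 10, prior Beta(0.01, 0.49) at each dose, rates ascending with dose, k=1. Take two rates with pL ≤ pH, the event at the start dose, and no events among the nH subjects. The posterior is proportional to

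pL^(0.01−1) (1−pL)^(0.49−1) × pH^(0.01−1) (1−pH)^(0.49−1) × pL (1−pL)^(nL−1) × (1−pH)^nH, for pL ≤ pH,

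and the risk is 1 − E[(1−pL)^(10−nL−nH)]. Numerical integration agrees with all 35 printed cells to within about 0.6 percentage points, which is consistent with simulation noise in the protocol's MCMC. The table is sound; only the count fed into it is in question.

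For 8 evaluable subjects:

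| nH | nL | Appendix 1 (%) | Recomputed (%) | Decision at 15% |
|---|---|---|---|---|
| 0 | 8 | 16.6 | 16.7 | Wait |
| 1 | 7 | 14.6 | 14.7 | Escalate |
| 2 | 6 | 13.9 | 13.8 | Escalate |
| 3 | 5 | 13.1 | 13.1 | Escalate |
| 4 | 4 | 12.9 | 12.7 | Escalate |
| 5 | 3 | 12.5 | 12.3 | Escalate |
| 6 | 2 | 11.9 | 12.0 | Escalate |
| 7 | 1 | 11.8 | 11.7 | Escalate |

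**Where the decision changes.** With 5, 6 or 7 evaluable, every split is Wait (lowest printed risk 18.4%). With 9, every split is Escalate (highest 8.3%). Only 8 evaluable depends on the split, and there only nH=0 gives Wait. Counting all pairs in which the printed-day nH exceeds the true nH, for 5 to 9 evaluable: 10 + 15 + 21 + 28 + 36 = 110. Seven change the decision, all with 8 evaluable and true nH=0. The excess over the cap is 16.6 − 15 = 1.6 points. With k=0 nothing changes, because only nL+nH ≥ 5 is required and moving a subject between the counts leaves the sum alone.

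**When it could happen.** No accrual rate is given, so assume one first dose every g days and that the first-enrolled subject is titrated. In days from that subject's first dose:

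- cohort filled at 9g;
- eighth subject evaluable at 7g+14, ninth at 8g+14;
- first subject in nH at 56 by the printed day, correctly at 70.

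The window in which the decision is wrong is min(8g+14, 70) − max(9g, 7g+14, 56). It is positive only for 5.25 < g < 7.78, that is, a cohort filled in about 47 to 70 days.

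- g=6: 62 − 56 = 6 days
- g=7: 70 − 63 = 7 days
- g=7.5: 70 − 67.5 = 2.5 days

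If the second-enrolled subject is the first to be titrated, the range is 6 < g < 8.75. Uneven enrolment can widen the window to the full 14 days of misclassification.

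**The case against.** The definition's own words run from the first titration dose, and only the parenthesis is wrong. The table footnotes give no day, 3.1.1 rules Day 43 out, and infusions are given at the site, so actual dates are known. A team using them counts correctly. This stands: the harm arises only if the printed day is applied.

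The scenario is also narrow. It needs exactly one AE of interest, exactly 8 evaluable, at least one titrated subject on Days 57 to 70 and none beyond, and a new subject waiting. Taking the 2% prior mean as a fixed rate, exactly one event in 10 subjects has probability 10 × 0.02 × 0.98^9 ≈ 17%, before the other conditions. Under even spacing with the first-enrolled subject titrated, a printed-day nH of 3 cannot occur: it would need 2g+56 below both 8g+14 (g > 7) and 70 (g < 7). Only nH of 1 or 2 arises there; 3 to 7 need clustered enrolment. The 7 of 110 is a count of table cells and carries no likelihood. This stands too.

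Finally, escalation is not automatic. The DMC reviews safety data before the next cohort (Protocol 7), the study team and investigator may halt escalation after a single SAE (3.1.3), and the early decision can be modified by agreement (3.1.4). These limit the consequence. None of them corrects the count on which the recommendation rests.

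**Conclusion.** The rule is wrong as written and should be corrected. The date conflict is certain from the current text of the protocol and SAP. Its effect is bounded: where the decision changes, the table's own risk is 16.6% against a cap of 15%. The panel would open at most about 14 days early, because a ninth evaluable subject without a further event, or one titrated subject truly reaching Day 71, would make Escalate correct.

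The change of decision rests on the printed day being applied and on the k=1, 8-evaluable, true nH=0 situation. The timing ranges rest on evenly spaced enrolment, which the documents do not state. The objections reduce the size of the problem but leave a wrong date in a safety rule that is printed in three places.

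**What to change.** In the nH and nL definitions in the synopsis, Protocol 3.1.4 and Appendix 1, replace Day 43 with the date of the subject's first infusion at the higher dose (planned Day 57, so that evaluation completes on Day 71). State that a titrated subject stays in nL until then. Tying the rule to the actual infusion date also covers delayed doses. The Appendix 1 risk table and Table 3.1.4-1 need no change.

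The cost is a wording amendment in three places. In the 8-evaluable situation, early escalation may wait up to two more weeks.

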3.1.3 Dose escalation for dose panel and stopping rules

Decisions regarding dose escalation will be made based on the review of all cumulative safety information which includes, in general, the safety data through study Day 15 from the 10 subjects in the preceding lower dose cohort. If neither of the below stopping rules is present in dose panel, then dose escalation may proceed within the next higher dose level. However, escalation to the next higher cohort may occur when none of the stopping rules have been met and no less than 5 subjects in a cohort have been followed for at least 2 weeks under certain conditions as illustrated in [section 3.1.4](#).

The stopping rules listed below will be used to determine whether it is safe to escalate to the next higher cohort. Dose escalation to the next planned dose will not proceed if any of the following criteria are met (Adverse event grading as defined by the Common Terminology Criteria for Adverse Events [CTCAE, Version 4.0]):

- Five or more subjects in a cohort have platelet counts $>450,000/\text{mm}^3$ for non-splenectomized subjects and $>600,000/\text{mm}^3$ for subjects who underwent splenectomy, and platelet count raise is not attributable to a rescue or concomitant therapy.
- Two or more subjects have serious adverse events in the same organ system (Grade 3 and above), that are determined to be related to study medication,
- It is determined that the limit of safety and/or tolerability has been reached. This decision will be made following discussions between the Study Team and the Investigator,

If any of the above criteria are met within a dose level, the progression to a higher dose level will be put on hold and all safety data available across the study will be evaluated to estimate the risk of proceeding to the higher dose level. The review will include all of the subject(s) that experienced SAEs listed above. In addition, data set may include subjects from a dose panel, the entire dose panel, or if appropriate, all randomized subjects treated to date.

In addition, decision may be made following discussions between the Study Team and the Investigator to halt dose escalation for reasons not defined above, including but not limited to, observing a single serious adverse event in individual subjects, observing trends in a given dose panel and across dose panels, and/or it is determined that the limit of safety and/or tolerability has been reached.

[figure not shown]

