Early Decision Rule:

If there is not AE of interest observed, the early decision rule is the same the minimum requirements.

If there is one AE of interest observed, the early decision rule is shown below in Table 3.1.4-1, where W represent wait, i.e., not enough evidence to enable dose panel escalation, and E represents escalate.

If there are least two subjects with AE of interest, stopping rule is triggered, and subject cannot be treated at the next higher cohort.

Table 3.1.4-1: Decision Rule for Early Panel Escalation When There Is One Subject with AE of Interest (k=1)

Titration-Dose Evaluable Subjects (nH) ^a	Start-Dose Evaluable Subjects (nL) ^b								
	1	2	3	4	5	6	7	8	9
0	W ^c	W	W	W	W	W	W	W	E ^d
1	W	W	W	W	W	W	E	E	
2	W	W	W	W	W	E	E		
3	W	W	W	W	E	E			
4	W	W	W	E	E				
5	W	W	E	E					
6	W	E	E						
7	E	E							
8	E								

^a the number of subjects who are titrated and complete the evaluation period (2 weeks) starting from the titration’s first dose.

^b the number of subjects who develop AE of interest or complete the evaluation period (2 weeks) from the first dose but could not be classified into the “Titration-Dose Evaluable Subjects” group.

^c W: Wait

^d E: Escalate

Physical examinations, vital sign measurements, 12-lead electrocardiograms (ECG), and clinical laboratory evaluations will be performed at selected times throughout the dosing interval. Subjects will be closely monitored for adverse events throughout the study. Blood samples will be collected for up to 336 hours after study drug administration for pharmacokinetic (PK)

analysis. Approximately 910 mL of blood will be drawn from each subject during the short-term period (~162 days including Screening and follow up period). Less than 500mL of blood will be drawn during the LTE period.

The approximate duration of the short-term period is 23 weeks (approximately 162 Days). This includes a 21 day screening period, a 12 week treatment period and a 2 month follow up period. An extended screening period (up to 42 days) is possible but only with the approval of the Study Director, and all other eligibility rules and screening rules must still be met. If subject is eligible and opts to continue into LTE, the 2 month follow-up period will not be performed after the short-term period is completed and the subject will enter the LTE directly. If the subject opts not to enter the LTE, then a 2 month follow-up visit will be completed.

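### The 15% decision-risk limit for early panel escalation is derived for one affected subject, but the same table also governs two subjects with serious events in different organ systems

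*Protocol*

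**What the plan says.** Section 3.1.4 describes the early rule as "controlling the probability of making a wrong early decision, called decision risk, to be at most 15" percent. Its count k is "the largest number of subjects who developed drug-related SAE within the same organ system at grade 3 or higher", restricted to 0 or 1; the Synopsis has the same definition. This matches the stopping criterion in 3.1.3: "Two or more subjects have serious adverse events in the same organ system (Grade 3 and above", where the events are judged related to study drug.

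For k=1 the decision is read from Table 3.1.4-1, by nH (titrated subjects evaluated at the higher dose) and nL (start-dose evaluable subjects). The table's title refers to one subject with an AE of interest. Appendix 1 derives the risk behind it as the chance that at least one pending subject adds an AE of interest to the one already seen.

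The definition of nL differs between two places. The text of 3.1.4 (also the Synopsis and Appendix 1) has "the number of subjects who develop drug related SAE at grade 3 or higher or complete the evaluation period", with no organ-system limit. Footnote b of the table has "the number of subjects who develop AE of interest or complete the evaluation period (2 weeks) from the first dose".

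Two places in Appendix 1 depart from the same-system wording. Under Decision Risk, the non-adaptive rule is described as allowing at most one subject with a drug-related serious event or serious infection. Under Decision Data, k is worded without the largest-count-in-one-system qualifier.

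**The concern.** Suppose two subjects each have a related Grade 3+ SAE, in different systems. The largest same-system count is 1, so the SAE stopping criterion is not met and the k=1 table applies. Its risk was computed for one event and one route to a stop. In this state a pending subject can complete a stop in either of two systems, and the second affected subject enters the calculation as event-free. Appendix 1 gives no risk for this state, yet a team reading E from the table would take the 15% control to apply.

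The nL conflict adds to this. On the 3.1.4 wording, a pending subject whose SAE is in a second system moves into nL at once while k stays 1, exactly as an event-free completion would. At boundary cells that changes W to E. On the footnote b wording it is unclear whether the subject enters nL before completing two weeks. The missing risk is a gap on either reading.

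**Working it through.** **1. Inputs (Appendix 1).** Cohort of 10; pending subjects m = 10 - nH - nL; prior Beta(0.01, 0.49) at each dose; event rate rising with dose; limit 15%. The prior was informed by drug-related SAEs of any system (12 of 721). No share per organ system is given.

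**2. Reproducing the printed k=1 risks.** Let p1 be the start-dose rate and p2 the next-dose rate, each Beta(0.01, 0.49), restricted to p1 <= p2, with one event in nL and none in nH:

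risk = E[1 - (1 - p1)^m]

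This matches all 35 printed cells within 0.6 points and the 16 E cells within 0.23 points. Example: (nH=1, nL=7) gives 14.7% against 14.6% printed.

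**3. Two events in different systems, both in nL.** Two of the 16 E cells, (7,1) and (8,1), cannot hold two start-dose events, which leaves 14. The plan does not say how to model this state, so two assumptions bracket it:

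- (a) Two independent systems, each carrying the printed risk r: 1 - (1 - r)^2. At (1,7): 1 - 0.854^2 = 27.1%.
- (b) One pooled rate with two events in nL, and a share s of new events falling in an affected system: E[1 - (1 - s*p1)^m].

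| Cell (nH,nL) | Pending | Printed % | (a) % | (b) s=1 % | (b) s=0.5 % | s at which (b) reaches 15% |
|---|---|---|---|---|---|---|
| (1,7) | 2 | 14.6 | 27.1 | 32.5 | 17.5 | 0.424 |
| (2,6) | 2 | 13.9 | 25.9 | 31.4 | 16.9 | 0.441 |
| (3,5) | 2 | 13.1 | 24.5 | 30.6 | 16.5 | 0.453 |
| (4,4) | 2 | 12.9 | 24.1 | 30.1 | 16.1 | 0.462 |
| (5,3) | 2 | 12.5 | 23.4 | 29.7 | 15.9 | 0.470 |
| (6,2) | 2 | 11.9 | 22.4 | 29.3 | 15.7 | 0.476 |
| (0,9) | 1 | 8.3 | 15.9 | 18.2 | 9.1 | 0.826 |

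The other seven one-pending cells give 11.1-13.9% under (a), and 14.9-16.9% under (b) at s=1.

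Cells above 15%: 7 of 14 under (a). Under (b), 13 at s=1, 6 for s from 0.48 to 0.82, and none at s of 0.42 or less. At s=0.4 the maximum is 14.2%. If S systems were equally likely, s = 2/S: S=4 gives a maximum of 17.5%, S=5 gives 14.2%, S=27 gives 2.8%.

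**4. One event in nL, one in nH.** At most 14.8% under (a). Under (b), 22.5% with two pending and 11.3% with one at s=1, and at most 12.0% at s=0.5.

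**5. Boundary cells.** Raising nL by one at fixed nH changes W to E in seven places (printed risk, %): (0,8) to (0,9), 16.6 to 8.3; (1,6) to (1,7), 22.7 to 14.6; (2,5) to (2,6), 21.1 to 13.9; (3,4) to (3,5), 20.0 to 13.1; (4,3) to (4,4), 19.3 to 12.9; (5,2) to (5,3), 19.3 to 12.5; (6,1) to (6,2), 18.4 to 11.9.

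**6. How often.** Given a cell, with per-subject rate q and S equally likely systems (both assumed), the chance that exactly two subjects have events, both in nL and in different systems, is C(nL,2) q^2 (1-q)^(nH+nL-2) (1-1/S). At (1,7) with q=0.02 and S=5: 21 x 0.0004 x 0.98^6 x 0.8 = 0.6%. For S from 5 to 27, q=2% gives 0.03% at (6,2), 0.6-0.7% at (1,7) and 1.0-1.2% at (0,9). At q=5% the figures are 0.15-0.18%, 3.1-3.7% and 5.0-6.1%.

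**The case against.** **A breach of 15% is not shown.** A reader might infer from the 22-33% figures that the limit is violated. The documents do not support that. Setting s=1 counts any new related SAE as a match, which is not the plan's same-system rule. Assumption (a) gives each system the whole of a prior informed by events in any system. With five or more equally likely systems no cell passes 15%. The model also gives each pending subject full risk even if part of the two-week window has passed. If half the window remained (assumed, constant hazard), (1,7) would cross at s = 0.424/0.5 = about 0.85. The printed risks make the same simplification. All of this stands. It leaves the risk unknown, which is different from shown to be at most 15%.

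**The W-to-E change is ordinary behaviour.** A reader might also infer that a second SAE itself pushes the table towards escalation. But any pending subject who becomes evaluable crosses the same seven boundaries, including one who completes two weeks without an event. The fall in printed risk is the gap between adjacent cells. An SAE in a subject already counted leaves the cell unchanged, and footnote b may keep the second-system event out of nL. This stands. What remains is that such an event is treated like an event-free completion, under a definition that the protocol states in two ways.

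**Safeguards exist.** With all 10 subjects evaluated, these two events would still not meet the numeric SAE criterion. Section 3.1.3 requires review of all cumulative safety data and allows a halt after a single serious event. For the table, 3.1.4 says "its decision can be modified upon agreement from both investigators and sponsor". Section 7 has the DMC review safety data before each cohort. These limit the practical harm but are matters of judgement and do not supply the missing risk.

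**Conclusion.** The point holds as a gap in what the 15% limit covers. By the definition of k in 3.1.4, two subjects affected in different systems are sent to a table derived for one, and Appendix 1 offers no risk for them. In the six two-pending E cells, with both events at the start dose, the risk could be anywhere from under 15% to about 33%, depending on the share of new events that fall in an affected system. The documents do not give that share; the first cell crosses at about 42%. The nL discrepancy is a real inconsistency with a limited effect. The state is rare, at about 1.2% or less for a given cell if the per-subject rate is 2%, and the override, cumulative review and DMC reduce its consequence. The change is still worth making, because this is a safety rule with a stated numerical control and the correction is cheap.

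**What to change.** State in 3.1.4 and Appendix 1 that the k=1 table and its 15% limit apply only when exactly one subject in the cohort has a related Grade 3+ SAE. With two or more such subjects in different systems, wait until all 10 have completed the two-week evaluation, or use a risk recomputed for that state against the same 15% limit, with its per-system assumption written down. Align three wordings with 3.1.3 and 3.1.4: footnote b of Table 3.1.4-1, the description of the non-adaptive rule under Decision Risk in Appendix 1, and k under Decision Data.

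Cost: three wording changes and one added statement. The existing simulation has to be rerun only if the recomputed-risk option is chosen. The downside is that the next cohort may open up to about two weeks later in a rare state, including cases whose true risk is below 15%.
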